5.2. Recording of Adverse Events

At each contact with the subject, the investigator will seek information on adverse events by specific questioning and, as appropriate, by examination. Information on all adverse events will be recorded immediately in the source document, and also in the appropriate adverse event module of the case report form (CRF). All clearly related signs, symptoms, and abnormal diagnostic procedures results will be recorded in the source document, grouped under one diagnosis when appropriate.

All adverse events occurring during the study period will be recorded. The clinical course of each event will be followed until resolution, stabilization, or until it has been determined that the study treatment or participation is not the cause.

Serious adverse events that are still ongoing at the end of the study period will be followed up to determine the final outcome. Any serious adverse event that occurs after the study period and is considered to be possibly related to the study treatment or study participation will be recorded and reported immediately.

*Adverse events will be reported to The Children’s Hospital of Philadelphia IRB [contact]) and CTTC [contact]), and the FDA (in writing only) annually at the time of continuing review.

Any action resulting in a temporary or permanent suspension of this study (e.g. FDA actions, IRB actions, or actions by a commercial sponsor or by the investigators or co-investigators) will be reported to BioMarin, Pharmaceutical Inc.

5.3. Reporting of Serious Adverse Events

5.3.1. Study Sponsor Notification by Investigator

An adverse event that is serious, related and unexpected, will be reported to the agencies cited previously by telephone or MEMO within 24 hours of the event. A Serious Adverse Event (SAE) form will be completed by the sponsor-investigator and faxed to the above agencies/regulatory bodies, according to current reporting requirements. The investigator will keep a copy of this SAE form on file at the study site. Report serious adverse events by phone and facsimile to:

The Children’s Hospital of Philadelphia IRB [contact])
 The Children’s Hospital of Philadelphia CTTC [contact])
 FDA (in writing only)

At the time of the initial report, the following information will be provided:

- Study identifier
- Subject number
- A description of the event
- Date of onset
- Current status
- Whether study treatment was discontinued
- The reason why the event is classified as serious
- Investigator assessment of the association between the event and study treatment

Within the following 48 hours, the investigator will provide further information on the serious adverse event in the form of a written narrative. This will include a copy of the completed Serious Adverse Event form, and any other diagnostic information that will assist the understanding of the event. Significant new information on ongoing serious adverse events will be provided promptly to the agencies cited.

5.4. Dose Escalation Decisions

Treatment cohorts will be dosed in escalating order as outlined above (section 3.4). Dose escalation decisions will be made by the investigator only after the safety of the previous dose level has been established. Subsequent cohorts will not be dose until safety data are obtained from all subjects in the previous cohort. Safety will be evaluated based on the incidence and severity of adverse events (AEs), clinical laboratory test results, ECGs, and other relevant clinical findings (e.g., heart rate, blood pressure, respiratory rate and temperature). Decisions to dose escalate or halt dose escalation will be based on review of these data by the investigator, the Safety Officer and the pharmacologist.

5.5. Stopping Rules

Subject Specific Stopping Rules

All subjects will be monitored during administration of the investigational product and if any of the events below occur the subject will be discontinued from treatment and followed clinically.

1. Subjects who have a wheal and flare reaction in the 30 minutes following peptide injection for the Hypersensitivity Test will be withdrawn from further investigation due to a positive hypersensitivity test and any further research procedures will be canceled.
2. **Peptide stopping rules:** Should any of the following events occur during administration of the investigational agent, in the setting of a serious adverse event or adverse event that is possibly related to exendin-(9-39), the subject's treatment will be discontinued and the subject will be followed clinically.
 - i. Blood pressure instability
 - ii. Pulse instability
 - iii. Fever

Trial stopping rules:

If 2 subjects experience serious adverse events thought to be probably or definitely related to study procedures or medications we will place the study on a voluntary hold to evaluate safety and study design. The IRB, FDA, and the Safety Officer will be informed and consulted as appropriate and per local and federal regulations.

Potential study related SAEs include the following:

1. Anemia requiring hospitalization as a consequence of the amount of blood being collected in study procedures
2. Severe hypersensitivity reaction requiring hospitalization

Surveillance of subjects will be performed to permit early detection of adverse events as discussed in the Data and Safety Monitoring Plan.

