Other than the effects on glucose homeostasis, which appears to be transient in human subjects, we do not anticipate other effects. Therefore, the anticipated benefits derived from these experiments which includes our understanding of the

physiopathologic role of GLP-1 in congenital hyperinsulinism, and moreover, the potential effect of exendin-(9-39) in controlling the severe hypoglycemia affecting these patients in face of the lack of effective medical therapy justify the proposed studies.

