 - a. Cohorts 1-2: at least 3 and up to 6 subjects per cohort, will be included in each of the first two cohorts. In any of the first 2 cohorts, if discontinuation of intravenous dextrose is achieved in 2 out of the 3 subjects up to three additional patients (at least 2 with diffuse disease, as defined by PET scan and/or genetics) may be enrolled in order to meet the Success Stopping Criteria (see 11a below).
 - b. Cohorts 3- 4: four subjects, with at least 2 subjects with diffuse disease. If discontinuation of intravenous dextrose is achieved in 1 or 2 of the 4 subjects, an additional subject with diffuse may be enrolled in order to meet the Success Stopping Criteria (see 11a below).

- c. The dose will be increased in $\frac{1}{2}$ log increments between cohorts as specified below:

Group	Dose Scheme (mg/kg/hr for 9 hours)	Total Dose (mg/kg)	Number of Subjects
1	0.2	1.8	3-6
2	0.6	5.4	3-6
3	2	18	3-5
4	6	54	4-6

11. Stopping Criteria:

- a. Success Stopping Criteria: the dose escalation will be stopped if in a cohort at least 2 subjects with diffuse disease are able to have dextrose infusion discontinued for the final 2 hours of the study period.
- b. Safety Stopping Criteria: if an exaggerated pharmacology effect is observed (blood glucose greater than 200 mg/dL for 2 hours off dextrose infusion) dose escalation will be stopped and the dosing algorithm will be modified to proceed with a dose that is 2 fold higher the previous level observed to be safe. Dosing will be stopped if any severe adverse event is observed.

12. Calculation of glucose infusion rate. Glucose infusion rate over the last 2 hours of the treatment period will be calculated by adding the total amount of intravenous glucose (in mg) received over 2 hours divided by the weight in Kg and by time (120 min).

13. Determination of therapeutic plasma levels, plasma half-life and pharmacokinetics of exendin-(9-39). During the infusion with exendin-(9-39) blood samples will be obtained at 1, 5, and 9 hours, and at 1 and 3 hours after the infusion ends. Should there be difficulty in establishing blood drawing lines to obtain samples of the secondary outcome variables the study will proceed with collection of the primary outcome variable only (glucose infusion rate). Plasma levels of exendin-(9-39) will be determined by mass spectrometry.

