4.4. Early Withdrawal of Subjects

4.4.1. When and How to Withdraw Subjects

Subjects will be withdrawn from the study if the test of hypersensitivity is positive upon admission before the initiation of the study protocol. Subjects will be withdrawn at any time during the study if an unexpected severe adverse event occurs. There are not expected safety concerns for abrupt termination of the study protocol.

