5.1. Definitions

Adverse Event

An **adverse event** (AE) is any symptom, sign, illness or experience that develops or worsens in severity during the course of the study. Intercurrent illnesses or

injuries will be regarded as adverse events. Abnormal results of diagnostic procedures will be considered to be adverse events if the abnormality:

- results in study withdrawal
- is associated with a serious adverse event
- is associated with clinical signs or symptoms
- leads to additional treatment or to further diagnostic tests
- is considered by the investigator to be of clinical significance

Serious Adverse Event

Adverse events will be classified as serious or non-serious. A ***serious adverse event*** is any AE that is:

- fatal
- life-threatening
- requires or prolongs hospital stay
- results in persistent or significant disability or incapacity
- a congenital anomaly or birth defect
- an important medical event

Important medical events are those that may not be immediately life threatening, but are clearly of major clinical significance. They may jeopardize the subject, and may require intervention to prevent one of the other serious outcomes noted above. For example, drug overdose or abuse, a seizure that did not result in in-patient hospitalization, or intensive treatment of bronchospasm in an emergency department would typically be considered serious.

All adverse events that do not meet any of the criteria for serious should be regarded as ***non-serious adverse events***.

Adverse Event Reporting Period

The study period during which adverse events must be reported is normally defined as the period from the initiation of any study procedures to the end of the study treatment follow-up. For this study, the study treatment follow-up is defined by the half-life of the drug and will be 24 hrs after the end of infusion.

Preexisting Condition

A preexisting condition is one that is present at the start of the study. A preexisting condition will be recorded as an adverse event if the frequency, intensity, or the character of the condition worsens during the study period.

General Physical Examination Findings

At screening, any clinically significant abnormality will be recorded as a preexisting condition. At the end of the study, any new clinically significant findings/abnormalities that meet the definition of an adverse event will also be recorded and documented as an adverse event.

Post-study Adverse Event

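### Item 11b's hyperglycemia event halts dose escalation, but no rule in the text expressly ties it to stopping the affected infant's own infusion

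*Combined protocol and SAP*

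**What the plan says.** Section 3.4, item 11b, on stopping for safety reasons: "if an exaggerated pharmacology effect is observed (blood glucose greater than 200 mg/dL for 2 hours off dextrose infusion) dose escalation will be stopped". The sentence goes on to reset the dose to twice the previous level found safe. The next sentence reads "Dosing will be stopped if any severe adverse event is observed".

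Section 5.5 holds the subject-specific rules. It says that subjects are monitored during administration and "if any of the events below occur the subject will be discontinued from treatment and followed clinically". The events listed are a positive skin test, blood pressure instability, pulse instability and fever. The last three count only alongside a serious adverse event or one possibly related to the drug.

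Section 4.4.1 adds: "Subjects will be withdrawn at any time during the study if an unexpected severe adverse event occurs".

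Section 3.4, item 8, sets a 9-hour infusion for every subject. Items 5 and 6 leave the intravenous dextrose rate as the only adjustment for glucose, with feeds continuing every 3 hours.

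**The concern.** The 11b event happens in one infant, yet both of its stated consequences concern other infants: whether the next cohort escalates, and at what dose. Subject-level stops belong in 5.5, and glucose is missing there. Once dextrose is off, the titration in item 5 has nothing left to reduce.

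The event is foreseeable. Section 3.5 gives the aim as removing the need for exogenous glucose altogether, so dextrose off is the intended state and 11b describes its overshoot. Section 1.4 reports two possibly related Grade 3 hyperglycemia events among the 31 subjects treated so far. They were transient, and no subject was withdrawn because of the drug. The new cohorts go well above the pilot doses, so that experience may not carry over.

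At stake is the safety of an infant who meets the protocol's own safety-stop definition and remains on drug. Consistency is also at stake: two infants with the same readings may be handled differently, depending on whether someone calls the event severe.

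**Working it through.** **Each rule set against the 11b event**

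- *11b, hyperglycemia clause:* acts on escalation and the next dose. It is silent on the running infusion.
- *11b, last sentence:* reaches the infant if the event is judged severe and if dosing means that infant's infusion. Section 5.1 says "Adverse events will be classified as serious or non-serious" and does not define *severe*. No grading scale is given, and no grade is mapped to that word.
- *4.4.1:* needs the event to be severe and unexpected. Section 1.4 says "Other than the effects on glucose homeostasis, which appears to be transient in human subjects, we do not anticipate other effects", which makes *unexpected* doubtful for high glucose.
- *5.5, subject list:* no glucose item.
- *5.4, 5.5 trial rules and 5.6.1:* govern decisions between cohorts, the trial as a whole and accrual, not one infusion.
- *5.1, abnormal laboratory values:* mentions discontinuing the drug as an example of active management. This recognises clinical judgement but sets no rule.

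**Exposure that a stop would avoid**

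Inputs: dose rates of 0.2, 0.6, 2 and 6 mg/kg/hr for 9 hours (3.4, item 10); half-life of 0.94 hr at a median weight of 5 kg (1.4). The plan's total doses reproduce: 0.2 x 9 = 1.8, 0.6 x 9 = 5.4, 2 x 9 = 18 and 6 x 9 = 54 mg/kg.

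Let t be the hour at which the 2-hour criterion is met. The documents do not give t. Hours 4 to 8 are an assumed working range. The outer limits are hour 2 (dextrose off and glucose above 200 from the start, an extreme case) and hour 9.

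Remaining dose = rate x (9 - t). Level at hour 9 relative to the level at the stop = 2^(-(9 - t)/0.94), assuming single-exponential decline although the plan's own model has two compartments.

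| t (hr) | Share of dose left | mg/kg left at 0.2 / 0.6 / 2 / 6 mg/kg/hr | Relative level at hour 9 if stopped |
|---|---|---|---|
| 2 | 7/9 = 78% | 1.4 / 4.2 / 14 / 42 | not computed |
| 4 | 5/9 = 56% | 1.0 / 3.0 / 10 / 30 | 2.5% |
| 6 | 3/9 = 33% | 0.6 / 1.8 / 6 / 18 | 11% |
| 8 | 1/9 = 11% | 0.2 / 0.6 / 2 / 6 | 48% |
| 9 | 0 | 0 | 100% |

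If the infusion continues, the level stays near plateau: on the same assumption, 1 - 2^(-4/0.94) = 95% is reached by hour 4. Stopping therefore lowers exposure substantially unless the event comes late.

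Dose multiples of the pilot maximum (0.1 mg/kg/hr): 0.2/0.1 = 2 up to 6/0.1 = 60.

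**The reset dose in 11b**

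Twice the previous level, against the triggering dose:

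- Cohort 1: 2 x 0.1 = 0.2 against 0.2 (100%), if Scheme #3 is the previous safe level
- Cohort 2: 2 x 0.2 = 0.4 against 0.6 (67%)
- Cohort 3: 2 x 0.6 = 1.2 against 2 (60%)
- Cohort 4: 2 x 2 = 4 against 6 (67%)

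The rule lowers the dose in cohorts 2 to 4. In cohort 1 it returns the dose that caused the event.

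**The case against.** A reader might infer that nothing in the plan can stop this infant's infusion, or that the protocol obliges staff to continue. The documents support neither. The last sentence of 11b speaks of dosing rather than escalation, and reading it to cover the running infusion is natural. A lack of definition does not disable that rule: 5.4 calls for review of severity, and 1.4 reports graded events. Clinicians can stop on judgement. The Data and Safety Monitoring Plan is listed as an attachment, was not in the text reviewed, and may hold the rule.

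The setting also limits the risk. Infants are in intensive care or an inpatient research unit with glucose checks every 30 minutes, the half-life is short, and 1.4 cites earlier short-term infusion studies that found no persistent effect after stopping. Two neonates given 0.1 mg/kg/hr for 6 hours showed no effect on glucose infusion rate.

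A reader might also take the remaining-dose figures as a measure of toxicity. They are part of the planned dose, and even the full 54 mg/kg keeps the plan's stated margins (1.9 to 2.2 by dose, 13 to 18 by AUC).

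All of this stands, and it narrows the point without closing it. Whether the defined safety event stops the infant's infusion depends on a word the protocol does not define.

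**Conclusion.** The concern holds in a limited form. No rule in the supplied text expressly links the 11b glucose event to stopping the affected infant's infusion. Only the general severe-event rules might, and their application here is a matter of judgement.

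On the assumed range of hours 4 to 8, between 11% and 56% of the 9-hour dose could still be given, up to 30 mg/kg in the top cohort. Over the outer limits the share runs from 0 to 78%. These figures rest on an assumed stop time and show avoidable exposure. They do not estimate extra hyperglycemia, and the documents give no basis for the event's frequency.

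The cohort 1 defect in the reset dose is separate and depends on Scheme #3 being the previous safe level. The changes are worth making because they are cheap and concern infants' safety.

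**What to change.** 1. Add a separate numbered item to the subject-specific rules in 5.5, outside the qualified peptide list: glucose above 200 mg/dL sustained for 2 hours with dextrose off means stop the infusion and follow clinically, whatever the severity grade or causality. Keep the 30-minute glucose checks and dextrose titration running afterwards, since glucose may fall as the drug clears. Cross-reference the item in 11b. If the Data and Safety Monitoring Plan already holds this rule, a cross-reference to it is enough.
2. For a stopped infant, take a PK sample at the stop and at 1 and 3 hours after it. Report the glucose infusion rate over the last 2 hours on drug, labelled as an earlier-window value. By the item 12 formula it is 0 mg / weight / 120 min = 0 mg/kg/min. Complete the vehicle day if it is still due, so that the pair is kept.
3. Amend 11b so that the modified dose must be below the triggering dose.

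**Cost.** One item, a cross-reference, one clause and a short analysis statement. Monitoring is already in place, and 4.4.1 says "There are not expected safety concerns for abrupt termination of the study protocol".

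The real price is data. The hour 7-9 on-drug glucose infusion rate is lost for that infant, and 4.4.2 does not supply it. The infant is a strong responder who makes up 1/6 = 17% to 1/3 = 33% of a cohort of 6 to 3. The earlier window may also fall at a different point in the 3-hour feeding cycle. The planned hour-9 PK sample is lost too, although section 3.5.2 labels the PK variables primary; the sample at the stop gives an end-of-infusion concentration for a shorter infusion. Finally, the infant cannot meet the final-2-hours success condition in 11a on drug, but 11b has by then already halted escalation.

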5.6. Medical Monitoring

It will be the responsibility of the Principal Investigator to oversee the safety of the study at this site. This safety monitoring will include careful assessment and appropriate reporting of adverse events as noted above, as well as the construction and implementation of a site data and safety-monitoring plan. Medical monitoring will include a regular assessment of the number and type of serious adverse events.

5.6.1. Data and Safety Monitoring Board

Given the nature of the study a Data and Safety Monitoring Board (DSMB) is not necessary. The attached data safety and monitoring plan include the establishment of a Safety Officer. The safety of the subjects enrolled on the study will be assessed by the Safety Officer. All SAE 's will be reviewed as they occur. Reporting requirements to the IND will be strictly adhered to. If more than one unexpected or previously undescribed serious adverse event attributable to exendin-(9-39) is observed, accrual to the protocol will be suspended. The Safety Officer will assess the risk to the subject, and a recommendation to continue with the study or close it will be made to the IRB for review. Should the decision be made to continue with the study, the modifications to the protocol, the updated assessment of risks and benefits, and a modified informed consent will be submitted to the IRB and FDA for consideration.

6. Data Handling and Record Keeping

6.1. Confidentiality

Information about study subjects will be kept confidential and managed according to the requirements of the Health Insurance Portability and Accountability Act of 1996 (HIPAA). Those regulations require a signed subject authorization informing the subject of the following:

- What protected health information (PHI) will be collected from subjects in this study
- Who will have access to that information and why
- Who will use or disclose that information
- The rights of a research subject to revoke their authorization for use of their PHI.

In the event that a subject revokes authorization to collect or use PHI, the investigator, by regulation, retains the ability to use all information collected prior to the revocation of subject authorization. For subjects that have revoked authorization to collect or use PHI, attempts will be made to obtain permission to collect at least vital status (i.e. that the subject is alive) at the end of their scheduled study period.

6.2. Source Documents

Source data are all information, original records of clinical findings, observations, or other activities in a clinical trial necessary for the reconstruction and evaluation of the trial. Source data are contained in source documents. Examples of these original documents, and data records include: hospital records, clinical and office charts, laboratory notes, memoranda, subjects' diaries or evaluation checklists, pharmacy dispensing records, recorded data from automated instruments, copies or transcriptions certified after verification as being accurate and complete, microfiches, photographic negatives, microfilm or magnetic media, x-rays, subject files, and records kept at the pharmacy, at the laboratories, and at medico-technical departments involved in the clinical trial.

6.3. Case Report Forms

The study case report form (CRF) is the primary data collection instrument for the study. All data requested on the CRF must be recorded. All missing data must be explained. If a space on the CRF is left blank because the procedure was not done or the question was not asked, write "N/D". If the item is not applicable to the individual case, write "N/A". All entries will be printed legibly in black ink. If any entry error has been made, to correct such an error, we will draw a single straight line through the incorrect entry and enter the correct data above it. All such changes will be initialed and dated. WE WILL NOT ERASE OR WHITE OUT ERRORS. For clarification of illegible or uncertain entries, we will print the clarification above the item, then initial and date it.

